## 1. Rationale

After having demonstrated a sedative effect (1), a multicenter, randomized, double-blind, sham-controlled trial has shown the efficacy and safety of external trigeminal nerve stimulation (e-TNS) with the Cefaly® device as preventive treatment of episodic migraine (2). Safety and patient satisfaction have been confirmed by a prospective study on 2,313 patients (3). The Cefaly® device was FDA-approved for migraine prevention in 2014.

More recently technical improvements with electrical parameters protocols and treatment protocols have allowed the development of an acute treatment of migraine attacks. Based on these innovations, and after a few pilot tests (4) (5), a Cefaly® Acute program has been tested in clinical trials for the acute treatment of migraine with or without aura.

- [name], at Columbia University, implemented an open-label pilot trial on the acute treatment of migraine with the Cefaly® e-TNS device (6). Thirty (30) patients having a migraine attack with or without aura were included in the modified intention-to-treat (mITT) analysis. In terms of safety, no adverse events or side effects were reported. In terms of efficacy, mean pain intensity was significantly reduced by 57.10% after the 1-hour e-TNS treatment ( $-3.22 \pm 2.40$ ;  $p<0.001$ ) and by 52.84% at 2-hour time point ( $-2.98 \pm 2.31$ ;  $p<0.001$ ). No patients took anti-migraine rescue medication within the 2-hour observation phase. Within the 24-hour follow-up, 34.62% of patients used a rescue medication. The findings from this open-label study suggest that e-TNS with the Cefaly® device is a safe and effective acute treatment for migraine, and merits further study with a randomized, double-blind, sham-controlled trial.
- University of Liege in Belgium (Prof. [name]) did a post-marketing survey on more than 800 regular users of the Cefaly® device in France, Switzerland and Belgium (7). 89.2% of responders to the questionnaire had been diagnosed by a physician as suffering from migraine. 88.6% of these patients reported to use the Cefaly® device during migraine attacks and that in 42.6% of these attacks, the use of the Cefaly® device prevented the intake of anti-migraine rescue medication.
- [name] conducted a multicenter, randomized, double-blind, sham-controlled trial on the acute treatment of migraine with the Cefaly® Acute device (9). One hundred and six (106) patients having a migraine attack with or without aura were randomized and included in the intention-to-treat (ITT) analysis. Among them, ninety-nine (99) were eligible for the modified intention-to-treat (mITT) analysis i.e. randomized patients having had the 1-hour stimulation treatment and having given their headache pain intensity measurement at baseline and at 1-hour time points. The last value carried-forward method was used when needed. In terms of safety, one adverse event (nausea) occurred but this event was minor and totally reversible (nausea resolved by itself after 20 minutes). There was no serious adverse events (SAE), nor were any subjective complaints or side effects reported in either group within the 24 hours after the beginning of the treatment. In terms of efficacy, in the

ITT analysis, the primary outcome, mean migraine pain intensity after the 1-hour e-TNS session compared to baseline, was very significantly more reduced in the verum group than in the sham group ( $-3.46 \pm 2.32$  versus  $-1.78 \pm 1.89$ ,  $p < 0.001$ ; or  $-59\%$  versus  $-30\%$ ,  $p < 0.001$ ). This pain relief percentage was as well significantly reduced in the verum group compared to the sham group at 2 hours and 24 hours. In the mITT analysis, mean migraine pain intensity was as well very significantly more reduced in the verum group than in the sham group at 1-hour ( $-3.83 \pm 2.13$  versus  $-1.85 \pm 1.89$ ,  $p < 0.001$ ; or  $-65\%$  versus  $-32\%$ ,  $p < 0.001$ ) and at 2-hour and 24-hour time points. In addition, the percentage of pain free patients at 24-hour time point was significantly higher in the verum group compared with the sham group (32% versus 13%,  $p < 0.05$ ), and 30% sustained pain relief for 24 hours was significantly higher in the verum group compared to the sham group (43% versus 21%,  $p < 0.05$ ). Anti-migraine rescue medication intake within the 24 hours after the beginning of the treatment was not significantly lower in the verum group.

Based on these trials providing safety and efficacy evidences for e-TNS with the Cefaly® device in the acute treatment of migraine, the Cefaly® Acute device was cleared by the FDA in September 2017 for the acute treatment of migraine with or without aura in patients 18 years and older.

Nevertheless, these safety and efficacy evidences were mainly reported for migraine patients treated in the clinic and for migraine lasting already for several hours. In order to get data with identical protocol design as usually carried out for abortive migraine medication triptans (i.e. treatment at home, on a migraine attack at an early stage of its development), a pilot trial has been implemented by [name] at Rochester Clinical Research, Inc., Rochester, New York, USA (10). The efficacy outcomes were very encouraging: 35.4% of patients were pain-free at 2 hours and 60.4% free from their most bothersome migraine-associated symptom, 70.8% had pain relief at 2 hours, sustained pain freedom and sustained pain relief at 24 hours were respectively 25% and 50%.

Consequently, there are enough evidences, pilot and Phase II data, to go for a Phase III multicenter, randomized, double-blind, sham-controlled trial on the acute treatment of migraine at home with e-TNS using a Cefaly® Abortive Program device.

## 2. Study objective

The main objective of this study is to have Phase III evidences of the efficacy of the Cefaly® Abortive Program device used at home for 2 hours to treat a migraine attack, as triptans are generally used. That is to say having randomized, double-blind, sham-controlled data of the efficacy and safety of the Cefaly® Abortive Program device in the abortive treatment of acute migraine as measured by 2-hour pain freedom, pain relief and migraine-associated symptoms freedom, plus evolution of these measurements for 24 hours after the beginning of the treatment session.

### 3. Study outcomes

#### 3.1. Efficacy outcomes

##### Primary outcomes:

1. Pain Freedom (PF) at 2 hours, defined as the percentage of patients having a reduction of a moderate or severe migraine headache (Grade 2 or 3) at baseline to no headache (Grade 0) at 2 hours after the beginning of the e-TNS session.
2. Most bothersome migraine-associated symptom (MBS) freedom at 2 hours, defined as the percentage of patients with absence, at 2 hours after the beginning of the e-TNS session, of the most bothersome migraine-associated symptom identified at baseline.

##### Secondary outcomes:

1. Pain Relief (PR) at 2 hours, defined as the percentage of patients having a reduction of a moderate or severe migraine headache (Grade 2 or 3) at baseline to a mild headache or to no headache (Grade 1 or 0) at 2 hours after the beginning of the e-TNS session.
2. Percentage of patients with absence of photophobia, phonophobia, nausea, vomiting at 2 hours after the beginning of the e-TNS session.
3. Use of rescue medication between 2 and 24 hours, defined as the percentage of patients who took anti-migraine rescue medication between 2 and 24 hours after the beginning of the e-TNS session.
4. Sustained pain freedom at 24 hours, defined as the percentage of patients having no headache (Grade 0) at 2 hours, with no use of anti-migraine rescue medication and no relapse of headache pain within the 24 hours after the beginning of the e-TNS session.
5. Sustained pain relief at 24 hours, defined as the percentage of patients having mild or no headache (Grade 1 or 0) at 2 hours, with no use of anti-migraine rescue medication and no relapse of headache pain within the 24 hours after the beginning of the e-TNS session.

Note: The baseline corresponds to the beginning of the e-TNS session.

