#### 4.2.2. Acute treatment phase

Included patient will be instructed to treat a single qualifying migraine headache within a 2-month period following the screening visit. A migraine headache is a qualifying migraine when all the following criteria are met:

1. The migraine headache severity is moderate or severe (Grade 2 or 3).
2. The migraine headache is associated with at least one of these migraine-associated symptoms: photophobia, phonophobia, nausea, vomiting.
3. The migraine headache started less than four hours ago.
4. No other migraine headache or headache has occurred in the previous 48 hours.
5. The migraine headache is not already resolving on its own i.e. the pain is not already diminishing.
6. No anti-migraine rescue medication has been taken since the beginning of the migraine headache.

In case of qualifying migraine, patient will have to apply the Cefaly® Abortive Program device (verum or sham) for a complete treatment session of 2 hours as soon as the migraine headache is moderate or severe (Grade 2 or 3).

In his/her paper diary, the patient will have to report the following data just before the start of the e-TNS treatment session (baseline data):

- if there is any aura with the qualifying migraine attack
- the headache pain severity on the following scale: 0 = no pain; 1 = mild pain; 2 = moderate pain; 3 = severe pain

---

 if the patient woke up with a migraine, the starting time of the migraine is considered to be at the time of wake-up.

- the migraine-associated symptoms (photophobia, phonophobia, nausea, vomiting) and will specify which associated symptom is the most bothersome symptom (MBS).

Two hours after the beginning of the treatment session, whatever its duration (normally just after removing the device and the electrode if the session ran correctly for 2 hours), the patient will have to report the following data (2-hour data) in his/her diary:

- the headache pain severity on the following scale: 0 = no pain; 1 = mild pain; 2 = moderate pain; 3 = severe pain
- the migraine-associated symptoms (photophobia, phonophobia, nausea, vomiting)

Patients will be instructed NOT to take any anti-migraine rescue medication during the 2-hour treatment session. Medication intake during the 2-hour treatment phase will be considered as a protocol violation.

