#### 8.2.2. Study hypotheses

The general hypothesis is that the Cefaly® Abortive Program device is safe and effective for the abortive treatment of migraine.

In particular, for the abortive treatment of migraine:

- 2 hours of e-TNS with the Cefaly® Abortive Program device is better than 2 hours of sham e-TNS to achieve pain freedom, as measured by the pain freedom at 2 hours and the sustained pain freedom at 24 hours.
- 2 hours of e-TNS with the Cefaly® Abortive Program device is better than 2 hours of sham e-TNS to achieve symptoms freedom, as measured by the MBS freedom at 2 hours and the absence of migraine-associated symptoms at 2 hours.
- 2 hours of e-TNS with the Cefaly® Abortive Program device is better than 2 hours of sham e-TNS to achieve pain relief, as measured by the pain relief at 2 hours and the sustained pain relief at 24 hours.
- Anti-migraine rescue medication intake is lower after 2 hours of e-TNS with the Cefaly® Abortive Program device than after 2 hours of sham e-TNS.
- No serious adverse events (SAE) due to the 2-hour e-TNS session with the Cefaly® Abortive Program device within the 24 hours following the beginning of the treatment.

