### 8.2.3. Statistical methods

- All relevant general, safety and efficacy data will be descriptively summarized at each time point.
- Continuous data will be summarized by the number of subjects (N), the arithmetic mean, the standard deviation, the coefficient of variation as a percentage (CV%), the median, the inter-quartile range, the minimum and the maximum value, when appropriate.
- Categorical data will be summarized by absolute (N) and relative (%) frequency tables.
- Where considered as relevant, the study data will also be graphically depicted.
- For each patient, the outcomes will be calculated according to all data available, and if necessary, imputation of missing data will be performed according to the last value carried forward method.
- Unless otherwise stated, all statistical tests will be conducted at the  $\alpha=0.05$  (2-sided) level.
- Comparison between two independent samples (verum and sham group) will be performed using either the Mann-Whitney U test (also called the Mann-Whitney-Wilcoxon (MWW), Wilcoxon rank-sum test, or Wilcoxon-Mann-Whitney test), the Fisher test or the Anova test.

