### 8.2.4. Statistical analysis

#### Efficacy analysis

The efficacy analysis will be executed on a modified intention-to-treat (mITT) basis.

Patient data will be included in the mITT analysis if all the four following conditions are met:

1. The patient treated a qualifying migraine.
2. The patient applied the Cefaly® Abortive Program treatment (verum or sham) during at least 30 minutes\*.
3. The headache pain severity score **AND** the migraine-associated symptom(s) at baseline were reported in the diary.
4. The headache pain severity score **OR** the migraine-associated symptom(s) at 2 hours were reported in the diary.

\*If the patient stopped the 2-hour treatment session after 30 minutes but before its end for any reason, he/she is kept in the modified intention-to-treat (mITT) analysis if all the other conditions are met.

If the patient takes anti-migraine rescue medication between 2 hours and 24 hours after the beginning of the e-TNS treatment session, the headache pain intensity and migraine-associated symptoms presence

can be affected by the medication and the last value carried forward method (2-hour value carried forward method in this case) will be applied for the 24-hour time point headache pain severity and migraine-associated symptoms.

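### Secondary outcome 2 does not say whether it is one composite or four per-symptom outcomes and sets no baseline condition; read per symptom, patients who never had the symptom count as free in both arms

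*Combined protocol and SAP*

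**What the plan says.** Section 3.1 gives secondary outcome 2 as "Percentage of patients with absence of photophobia, phonophobia, nausea, vomiting at 2 hours after the beginning of the e-TNS session". Neither the composite/per-symptom question nor a baseline condition is addressed there, and sections 8.2.3 and 8.2.4 add no denominator rule for it.

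The neighbouring outcomes are tied to a baseline state. Primary outcome 2 counts the absence "of the most bothersome migraine-associated symptom identified at baseline", and the pain freedom and pain relief outcomes start from Grade 2 or 3.

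Four other parts of the plan bear on the point:

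- Section 4.2.2 needs only one of the four symptoms for an attack to qualify: "The migraine headache is associated with at least one of these migraine-associated symptoms: photophobia, phonophobia, nausea, vomiting".
- Section 8.2.2 places this outcome under the hypothesis that the device is better than sham to "achieve symptoms freedom, as measured by the MBS freedom at 2 hours and the absence of migraine-associated symptoms at 2 hours".
- Section 8.2.4 limits the mITT set by, among other conditions, "The patient treated a qualifying migraine", and requires that the "migraine-associated symptom(s) at baseline were reported in the diary". At 2 hours, either the pain score or the symptoms is enough.
- Section 8.2.3 says that, where needed, "imputation of missing data will be performed according to the last value carried forward method". It lists the Mann-Whitney, Fisher and Anova tests for comparing the arms. No stratified test is named.

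**The concern.** Because one symptom is enough to qualify, a patient may lack any particular symptom at baseline. On a per-symptom reading, a patient who never had the symptom and does not develop it counts as free in both arms. The same holds if the 2-hour symptom entry is blank. The patient can stay in mITT on the pain score alone, and the baseline absence is carried forward as a success.

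The stated hypothesis is about achieving freedom, which a patient without the symptom cannot do. Such patients add a similar high success rate to each arm. The published freedom rates would then partly reflect how common the symptom was, the risk difference would tend to shrink, and the test would carry avoidable variance. Leaving the choice between composite and per-symptom open until the data are seen would also add an unplanned analysis choice.

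**Working it through.** **The plan's own figure.** The only sample size given is for 2-hour pain freedom (section 8.2.1): 35.4% v 22.0%, two-sided 5%, 90% power. The pooled two-proportion formula gives 237.4, so 238 per group against the stated 239. Power at 239 is 90.2%, and 239/0.80 = 298.75 gives the stated 299. The figure reproduces, and the same formula is used below. No power is stated for secondary outcome 2.

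**Inputs.** 240 per arm is 600 × 0.80 / 2. The documents give no baseline prevalence, symptom-specific freedom rate or onset rate. The following are therefore assumptions: freedom of 50% v 38% among patients with the symptom, 5% new onset in both arms among those without it, and prevalence q varied.

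**Per-symptom reading, all patients.** Rate = q × freedom + (1 − q) × 0.95. At q = 0.5:

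- verum: 0.5 × 0.50 + 0.5 × 0.95 = 72.5%
- sham: 0.5 × 0.38 + 0.5 × 0.95 = 66.5%

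A 12-point difference among patients with the symptom becomes 6 points overall.

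**Unstratified v stratified test at q = 0.5.** The unstratified standard error is √(2 × 0.695 × 0.305/240) = 0.0420, so z = 0.06/0.0420 = 1.43 and power is about Φ(1.43 − 1.96) = 30%. Stratifying by baseline presence keeps the same 6-point difference but removes the variance between strata: √((2/240) × (0.5 × 0.44 × 0.56 + 0.5 × 0.05 × 0.95)) = 0.0350. Then z = 1.71 and power is about Φ(1.71 − 1.96) = 40%. Simulating the CMH test (100,000 trials per row, no continuity correction) gives the same answer:

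| q | All-patient rates | Unstratified | CMH, all patients | Only those with the symptom |
|---|---|---|---|---|
| 40% | 77.0% v 72.2% | 23% | 31% | 39% |
| 50% | 72.5% v 66.5% | 30% | 40% | 46.5% |
| 60% | 68.0% v 60.8% | 38% | 49% | 54% |
| 80% | 59.0% v 49.4% | 56% | 64% | 66% |
| 90% | 54.5% v 43.7% | 66% | 70% | 71% |

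**If the device also prevents new onset.** Keep q = 0.5 and let verum onset be sham onset × 0.50/0.62, the same relative rate as persistence:

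| Sham onset | Unstratified | CMH | Only those with the symptom |
|---|---|---|---|
| 5% | 34% | 46% | 46.5% |
| 10% | 37% | 47% | 46.5% |
| 20% | 44% | 50% | 46.5% |
| 30% | 51% | 55% | 46.5% |

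At 30% onset the all-patient test overtakes restriction. The stratified test beats the unstratified one in every row.

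**A check closer to the plan's figures.** Take the pilot's 60.4% freedom from the most bothersome symptom (section 1) for verum, and 60.4 − 13.4 = 47.0% for sham, borrowing the 35.4 − 22.0 gap. With 239 per arm and no new onset, unstratified v CMH power is 76% v 80% at q = 0.9, 59% v 69% at 0.7 and 41% v 55% at 0.5. The relative risk of still having the symptom is 0.396/0.530 = 0.747, with or without the patients who never had it.

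**Composite reading.** If success means all four symptoms absent, section 4.2.2 and mITT conditions 1 and 3 mean that no analysed patient is a success at baseline. Then q = 1, the difference stays at 13.4 points in the last example, and power is 84% either way. A blank 2-hour entry carried forward scores as failure.

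**The case against.** The text fits a composite at least as naturally. It is a single numbered item, and section 8.2.2 names the symptoms collectively. On that reading the dilution disappears. This stands, and it limits the point: a reader might infer that the outcome certainly counts patients who never had the symptom, but the documents do not settle that. They do not exclude it either. The item lists four symptoms without saying that all must be absent, and sections 4.2.2 and 7.1 have them recorded by name.

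A reader might also infer that the definition shrinks any real effect. It does not. Without new onset the relative risk of persistence is unchanged, and prevention of new symptoms is a benefit that only the all-patient outcome captures. For the same reason, restricting to patients with the symptom is not free of loss. This objection stands against restriction as the only analysis. It does not stand against stratification with everyone kept.

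The prevalences are assumed. Section 4.2.2 permits absence of a symptom but does not show how often it occurs, so it cannot be said that many patients lack nausea. Where nearly all have the symptom, the loss is small.

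Finally, the outcome is secondary and was not powered, dilution runs towards no difference, and primary outcome 2 already gives a baseline-anchored symptom measure. All true. These facts limit the consequence but do not settle what the outcome means.

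**Conclusion.** The outcome is underspecified in two respects: composite or per symptom, and which patients form the denominator. On the per-symptom reading, patients who never had the symptom count as free in both arms. This raises the freedom rates and, when new onset is low or similar in the arms, shrinks the risk difference by roughly the prevalence of the symptom (12 points to 6 at 50%). Compared with a stratified test, the unstratified test gives up about 8 to 11 points of power at 40% to 60% prevalence and about 4 points at 90%. These sizes rest on the assumed 50% v 38% freedom, 5% onset and 240 per arm. The direction of the stratified v unstratified comparison held at every prevalence and onset rate tried.

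On the composite reading there is no dilution. In neither case are the type I error or the primary sample size affected.

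**What to change.** State in section 3.1, and match in section 8.2.2, whether secondary outcome 2 is absence of all four symptoms, four per-symptom outcomes, or both.

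For any per-symptom result:

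- Keep all mITT patients and compare the arms with a Cochran-Mantel-Haenszel test stratified by baseline presence of that symptom. Add this test to section 8.2.3.
- Show on separate lines the percentage free at 2 hours among patients with the symptom at baseline, and the percentage with new onset among those without it.
- Say how a blank 2-hour symptom entry is scored, so that a carried-forward baseline absence does not count as freedom achieved.

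No new data are needed, since mITT condition 3 already requires baseline symptoms. The cost is wording and one or two extra table lines per symptom. Denominators will be small for rare symptoms: if vomiting were present in 5% at baseline (an assumption), 240 × 0.05 = 12 patients per arm would remain on the freedom line, too few for a useful comparison.

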#### 4.2.3. Post-treatment phase

Starting two hours after the beginning of the treatment session, the patient is allowed to take anti-migraine rescue medication if and only if the migraine headache pain is moderate or severe, either because there has not been pain relief or because after initial pain relief (no headache or mild headache pain) a moderate or severe headache is resuming.

The patient will have to report the following data in his/her diary at 24 hours after the beginning of the treatment session (24-hour data):

- the rescue medication intake, if any, between 2 hours and 24 hours after the beginning of the treatment session, and, if applicable, the time when the medication was taken
- the headache pain severity on the following scale: 0 = no pain; 1 = mild pain; 2 = moderate pain; 3 = severe pain

- the migraine-associated symptoms (photophobia, phonophobia, nausea, vomiting)

In his/her AE reporting form, the patient will record any adverse event occurring during the 24 hours following the beginning of the treatment session and is instructed to notify the investigator immediately for any serious adverse event with the stimulation.

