## 7. Practical study modalities

### 7.1. Efficacy outcome measures

The treatment efficacy outcomes will be assessed based on the following clinical data.

- **Headache pain severity.** In order to evaluate the modification of pain severity from baseline to 2-hour and 24-hour time points, patients will be asked to note their headache pain intensity on the following scale: 0 = no pain; 1 = mild pain; 2 = moderate pain; 3 = severe pain.
- **Migraine-associated symptoms.** The patient will also note the presence of migraine-associated symptoms (photophobia, phonophobia, nausea, vomiting) and will specify which associated symptom is the most bothersome symptom (MBS) at baseline.
- **Rescue medication intake.** The patient will also record whether he/she took ANY anti-migraine rescue medication during the 24 hours following the beginning of the e-TNS treatment session.

The following table depicts when the different measures will be made:

	At baseline, i.e. just before the beginning of the e-TNS session	2 hours after the beginning of the e-TNS session	24 hours after the beginning of the e-TNS session
Headache pain severity	•	•	•
Migraine-associated symptoms	•	•	•
Identification of the most bothersome migraine-associated symptom (MBS)	•		
Rescue medication intake			•

All clinical data will be collected on a paper diary and AE reporting form.

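### The sustained outcomes require no relapse up to 24 hours, but pain after baseline is recorded only at 2 and 24 hours and relapse is undefined, so an unrescued relapse that clears is counted as a success

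*Combined protocol and SAP*

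**What the plan says.** Section 3.1 defines sustained pain freedom (secondary outcome 4) as Grade 0 at 2 hours, and sustained pain relief (secondary outcome 5) as Grade 0 or 1 at 2 hours. Both add the same condition: "no use of anti-migraine rescue medication and no relapse of headache pain within the 24 hours after the beginning of the e-TNS session". That condition covers the whole interval, not just its end.

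The data to be collected are itemised in three places:

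- Section 4.2.2: pain grade and associated symptoms, first just before the session and then again: "Two hours after the beginning of the treatment session, whatever its duration".
- Section 4.2.3: one diary entry at 24 hours, with current pain grade, current symptoms, and "the rescue medication intake, if any, between 2 hours and 24 hours after the beginning of the treatment session", including the time of intake.
- Section 7.1: pain grades are collected for this purpose: "In order to evaluate the modification of pain severity from baseline to 2-hour and 24-hour time points". The table there has three columns (baseline, 2 hours, 24 hours) and no row for recurrence.

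Section 4.2.3 permits rescue after 2 hours "if and only if the migraine headache pain is moderate or severe", and section 6.6 repeats the restriction. One of the two situations it describes is that "after initial pain relief (no headache or mild headache pain) a moderate or severe headache is resuming". Relapse is not defined anywhere, and sections 8.2.3 and 8.2.4 give no rule for deriving it.

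**The concern.** The definition needs to know whether headache came back at any time between 2 and 24 hours. The diary items reveal this only if the patient took medication or still had pain at 24 hours. A relapse that was neither treated nor still present leaves no trace, and the patient is scored as sustained. For sustained pain freedom, a return to mild pain is especially hard to see, because permitted rescue is limited to Grade 2 or 3.

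The undefined term is a second gap. Even with complete data, two analysts could classify the same patient differently.

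Section 8.2.2 names sustained pain freedom and sustained pain relief as measures of the efficacy hypotheses, and section 2 puts the course over 24 hours into the main objective. What is at stake is whether these two reported rates mean what their definitions say.

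**Working it through.** **1. Definition against data.** Examples of patients who take no rescue medication:

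| 2 h | Between | 24 h | Definition | Recorded data |
|---|---|---|---|---|
| Grade 0 | returns to Grade 2, clears | Grade 0 | relapse: not sustained | counted as sustained |
| Grade 0 | returns to Grade 1, clears | Grade 0 | not sustained pain-free if any headache is a relapse | counted as sustained |
| Grade 1 | rises to Grade 2, settles | Grade 1 | not sustained relief if Grade 2 is a relapse | counted as sustained |
| Grade 0 | not known | Grade 1 | open: relapse undefined | open |

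A related route: entry to the modified intention-to-treat set (section 8.2.4) requires baseline and 2-hour data but no 24-hour data, while under section 8.2.3 "imputation of missing data will be performed according to the last value carried forward method". A 2-hour responder with a blank 24-hour pain grade could therefore be given the 2-hour grade and count as sustained. Carrying the 2-hour value forward after rescue creates no false success, because rescue already fails the definition.

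**2. The plan's own figure.** Section 8.2.1 gives 239 per group for 35.4% versus 22.0% pain-free at 2 hours, two-sided 5%, power 90%. With pooled variance and no continuity correction:

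n = [1.960 × √(2 × 0.287 × 0.713) + 1.282 × √(0.354 × 0.646 + 0.220 × 0.780)]² / 0.134² = 237.4, so 238.

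Power at 239 is 0.902, and 239 / 0.80 = 298.75, so 299. The figure reproduces to within one patient. It rests on a 2-hour outcome and is untouched by this point.

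**3. Direction.** In each arm let p be the 2-hour response rate, v the share of responders visibly lost (rescue, or pain at 24 hours), and m the share with a missed relapse.

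- Counted rate = p(1 − v); true rate = p(1 − v − m).
- Overstatement in the arm = p × m, which is never negative.
- Overstatement of the difference = p(verum) × m(verum) − p(sham) × m(sham). This is positive when m(sham)/m(verum) < p(verum)/p(sham) = 35.4/22.0 = 1.61.
- If v and m are the same in both arms, the risk ratio is 1.61 both counted and true.

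**4. Illustration for sustained pain freedom.** Assumptions: the pilot's fall from 35.4% to 25% (section 1) is all visible loss, so v = 1 − 25/35.4 = 29.4%, and it applies to both arms. The values of m are also assumed.

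| m verum | m sham | Verum | Sham | Difference (points) |
|---|---|---|---|---|
| 0 (as counted) | 0 | 25.0% | 15.5% | 9.5 |
| 10% | 10% | 21.5% | 13.3% | 8.1 |
| 20% | 20% | 17.9% | 11.1% | 6.8 |
| 10% | 20% | 21.5% | 11.1% | 10.3 |

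Equal missed rates make the counted difference too large. In the last row it is too small, because the sham rate is twice the verum rate and so exceeds the 1.61 limit.

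**5. Illustration within one arm.** Suppose 5% to 30% of patients counted as sustained had an unseen relapse (assumed range), with 239 patients:

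- Counted 25% (pilot sustained pain freedom): true 23.75% to 17.5%, about 3 to 18 patients.
- Counted 50% (pilot sustained pain relief): true 47.5% to 35%, about 6 to 36 patients.

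**The case against.** Relapses that are treated, or still present at 24 hours, are caught. Both primary outcomes are 2-hour measures, and section 8.2.2 pairs each sustained measure with a directly observed 2-hour one. The investigator also reviews the diary at the final visit (section 4.2.4), and the adverse event form covers the same 24 hours. All of this limits the damage, and it is why the point does not reach the primary analysis. It does not close the gap: the review checks what was entered, and the plan neither asks for recurrence on either form nor says how it would enter the outcome. The diary form itself is not among the documents, but its contents are itemised in sections 4.2.3 and 7.1.

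For sustained pain relief, if relapse means reaching Grade 2 or 3, that is also when rescue is permitted and recorded. More patients are 2-hour responders for relief than for freedom (70.8% against 35.4% in the pilot), and a reader might infer that relief is the worse affected. The documents do not show this, because the undetected share may be smaller.

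A reader might also take the rescue rule in section 4.2.3 as a definition of relapse at moderate or severe pain. It is a condition for medication and does not use the word. The wording of outcome 4 more naturally means any return of headache. What stands is that the plan does not settle it.

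**Conclusion.** The gap is real and should be fixed. As written, outcomes 4 and 5 cannot be derived as defined, and the missed relapses can only overstate the sustained rate in each arm. The size cannot be computed, because the documents give no missed-relapse rate for either arm; the figures above are illustrations.

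Two stronger readings are tempting:

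- **That the error favours the device.** This holds for similar missed rates in the two arms, and at 35.4% versus 22.0% up to a sham rate about 1.6 times the verum rate. Beyond that it reverses. The documents do not say how the rates compare. With equal rates, only the absolute difference is inflated and the risk ratio is unchanged. If the arms also had the same 2-hour response and visible loss, no difference would be created.
- **That the difference is 17% to 40% too large** (9.46/8.12 = 1.17; 9.46/6.78 = 1.40). This rests wholly on assuming that 10% to 20% of 2-hour responders in both arms have missed relapses. That is already 14% to 28% of those counted as sustained (0.10/0.706 and 0.20/0.706). It also borrows the pilot's loss for both arms, although section 1 does not say how the pilot ascertained relapse.

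Only two secondary outcomes are affected. The primary outcomes and the sample size stand.

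**What to change.** Add one item to the 24-hour diary entry in section 4.2.3 and a matching row to the table in section 7.1: did headache return or worsen between 2 and 24 hours and, if so, the worst grade (0 to 3) and the time it started.

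Define relapse in advance for each outcome in section 3.1 and state the derivation in section 8.2.4. One workable choice is any grade above 0 after 2 hours for sustained pain freedom, and any grade above 1 for sustained pain relief. The threshold is the sponsor's to choose, but it has to be written down.

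If the diary cannot be changed, rename the outcomes as Grade 0 (or Grade 0 or 1) at both 2 and 24 hours without rescue medication, and drop the no-relapse wording.

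The cost is one diary line, one table row and a wording amendment. The downsides are an answer recalled over up to 22 hours, which brings its own error, and somewhat lower sustained rates in both arms. The fallback costs only wording but gives up the claim about the interval.
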